## Consent Process

This protocol will utilize a verbal consent process and meets criteria for a waiver of written consent as follows:

(1) The research involves no more than minimal risk to the subjects.

IRB determination of risk for initial protocol application is MINIMAL and protocol updates present no additional risk to participants.

(2) The waiver or alteration will not adversely affect the rights and welfare of the subjects.

Participants will receive the same information about their rights and autonomy to participate or not participate in research without any effect on their treatment or any other opportunities.

(3) The research could not practicably be carried out without the waiver or alteration.

Due to COVID-19 precautions, continuation of a hybrid (in-person/remote) protocol, and the time-sensitive nature of the research question, the altered consent process remains necessary to protect the health and safety of both participants and study staff. Because we will continue to offer participants with the option to conduct study activities remotely, we will administer verbal consent consistently across all remote and in-person participants. In-person participants will be offered paper copies of the consent form for their records. Remote participants will be offered a digital copy of the consent form via text or email or a physical copy provided during a routine visit to the clinic.

(4) Whenever appropriate, the subjects will be provided with additional pertinent information after participation.

We are requesting a verbal consent process. This process does not involve additional information given to participants after participation.

The consent process will take place after a participant is deemed potentially eligible based on initial screening questions and expressed interest in participation and before a potentially eligible participant proceeds with the baseline assessment. Participants will be reminded that they can stop participating in the study at any time, and that all aspects of this study are voluntary.

A trained research staff member will conduct the informed consent. Consent will be taken by reading consent forms to the participants over the phone, Google Voice, virtual conferencing platform (Zoom), or in-person. The researcher will read the consent form and the UMB COVID Risk Statement to the participant “word for word” or paraphrase – whichever makes the participant most comfortable. Prior to providing verbal consent, participants will be given the chance to ask questions, and the researcher or trained designee will answer all the questions, making sure that the participants are satisfied and comprehend study procedures. Participants will also be informed about the voluntary nature of the study, and their right to withdraw at any point. If the participant refuses to consent, they will be considered a

refusal and therefore ineligible for the study. The researcher or trained designee must witness verbal consent by the participant during the phone, web-based call, or in person.

Before the participant can provide verbal consent, the participant: 1) should verbalize understanding; 2) should be given the opportunity to ask questions; 3) should be given time to hear the consent; 4) should report all questions were answered to their satisfaction; and 5) must correctly answer the evaluation to provide consent document. When completing the evaluation to give consent form, the researcher or trained designee will ask questions 1 through 3 to ensure that the participant understands the risks, understands what will be expected of him/her, and understands that they may drop out at any point during the study.

After verbal consent is provided for both the study consent form and UMB COVID Risk Statement, the researcher will document participant ID number, researcher initials, verbal consent date and time, location of research team member, location of participant, means used (telephone, computer audio at UMDTC, or in-person), start and end time, quality of call (if remote), alternative form of communication established (if remote), and any barriers to effective communication in a database. This information will be stored in a secure, HIPAA compliant UMB drive (Sharepoint or Microsoft Teams).

All study personnel will be appropriately trained in the ethical conduct of human subjects research and will be required to recertify annually.

## Conflict of Interest

None

## HIPAA Compliance

All protected health information (PHI) will be stored on UMB's HIPAA compliant data storage server or as paper records in double-locked space at UMCP to which only authorized research personnel have access. Confidentiality is assured as participants will be identified on all study materials by only a participant number and date of visit. By recording the electronic study data in this manner the information is considered 'de-identified', and therefore, compliant with the Standards of Privacy of Individually Identifiable Health Information ("Privacy Rule") of the Health Insurance Portability Act of 1996 ("HIPAA").

Data Analysis Plan

Project Title: Adapting a Peer-Delivered Behavioral Activation Intervention to Improve Adherence to MAT among Low-Income, Minority Individuals with OUD

Principal Investigator: [name]

Grant: R61AT010799

Version Date: 21 September 2022

Primary Outcomes

Descriptive statistics were used to characterize the sample, including implementation outcomes. We defined benchmark milestones *a priori* for successful implementation: $\geq 75\%$ of patients participating in the first *Peer Activate* session (feasibility); $\geq 75\%$ of patients completing $\geq 75\%$ of the core *Peer Activate* sessions (acceptability); and PRS fidelity $\geq 75\%$ as rated by an independent coder. Methadone retention was examined using descriptive and inferential analyses.

Implementation Outcomes

Feasibility measured using qualitative feedback and quantitatively as the % of patients who agree to participate in the intervention.
 
Quantitatively, $\geq 75\%$ of patients agreeing to participate in the intervention will be considered feasible.
 
Qualitatively, feasibility as defined by Proctor's model and coded by two independent coders.

Acceptability measured using qualitative feedback and quantitatively as the % of patients enrolled who attend $\geq 75\%$ of the core sessions.
 
Quantitatively, $\geq 75\%$ of patients attending $\geq 75\%$ of the core sessions will be considered acceptable.
 
Qualitatively, acceptability as defined by Proctor's model and coded by two independent coders.

Fidelity measured based on peer adherence to the intervention manual. A random selection of 20% of sessions were rated for fidelity, and $\geq 75\%$ of session components delivered as intended will be considered the threshold for fidelity.

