This study builds upon our team’s formative work ([name], Gorka, MacPherson, et al., 2011; [name] et al., 2018; Satinsky, Doran, Felton et al., 2019) to adapt and evaluate BA delivered by PRSs (“Peer Activate”) to support MOUD retention for low-income, minoritized individuals initiating MOUD at an outpatient, opioid treatment program in a medically underserved community in Baltimore City. Baltimore is a prime location to test innovative strategies to combat the OUD crisis, as its overdose

fatality rate is among the highest in the US, particularly for low-income, African Americans (Hogan, Rutherford, & Neall, 2017; KFF, 2017; Baltimore City Health Department, 2018). Guided by Aarons' stage model (Aarons, Hurlburt & McCue Horwitz, 2011) and Proctor's model of implementation (Proctor et al., 2011), we propose a mixed methods, hybrid Type 1 effectiveness-implementation study:

Aim: To refine a PRS-delivered Peer Activate approach for delivery at a methadone treatment (MT) program. Specific aims are:

1. To establish feasibility (primary), acceptability, and fidelity of Peer Activate in an open-label trial (n=40), and to pilot assessment procedures, including collecting preliminary MOUD outcomes (retention, abstinence). We hypothesize Peer Activate will be feasible ( $\geq 75\%$  of patients agree to participate), acceptable ( $\geq 75\%$  of those enrolled complete  $\geq 75\%$  of the 5 core sessions) and delivered by PRSs with fidelity ( $\geq 75\%$  of a randomly selected 20% of session delivered as intended).
2. To refine and finalize training and therapy manuals/procedures based on findings.

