After discussing the study with the research team member by telecommunication (audio or video) or in-person and based on continued interest, the participant will be invited to complete the informed consent process (detailed below in Procedures) and to schedule the baseline assessment. In all cases, patients will be informed that the study provides gift card compensation for participation. The study team member will reiterate that participation in the study will in no way affect any services that they receive at UMDTC or elsewhere. They will also make the participation options, remote or in-person, clear and answer any question about COVID-19 safety concerns. The study team member will also work with the participant to understand their access to technology for study communication. The study team will work with each participant to try to accommodate their individual frequency needs (aiming for a minimum of every other week) for intervention and other study-related contact, with flexibility of timing based on each individual's dosing schedule and needs. The study team will keep a record of participant access to technology (e.g. phone minutes, texting capability, video capability, WiFi, etc.) in a UMCP REDCap database (non-identifiable information only) and in a HIPAA-compliant, UMB-based Microsoft Teams spreadsheet (includes identifiable contact information). As needed, the research team will provide information on/assistance with applying for a phone through public assistance programs and other resources available at UMDTC.

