## Enrollment Numbers

For the open-label trial, our goal is to have at least 30 patients initiate the intervention, and at least 24 completers.

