## Rationale for Enrollment Numbers

We will enroll at least 30 patients because we expect to have an attrition rate of approximately 20% based upon current retention rates in other research at this site and significant attrition between baseline and initiating the intervention. The minimum target size (n=30) is of patients who are receiving the intervention to be large enough to allow us to demonstrate feasibility, implementation, acceptability, and

preliminary efficacy for the intervention and also allow us to make any changes to the protocol if deemed necessary prior to collecting the full sample.

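### The SAP gives two different 75% benchmarks for feasibility, the protocol's primary outcome: agreeing to participate, and taking part in the first session

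*SAP*

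**What the plan says.** Aim 1 in the protocol's Abstract reads "To establish feasibility (primary), acceptability, and fidelity of Peer Activate in an open-label trial (n=40", and its feasibility hypothesis is that at least 75% "of patients agree to participate".

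The SAP states the benchmark twice under Primary Outcomes:

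- The opening paragraph lists milestones described as defined in advance. The feasibility milestone is at least 75% "of patients participating in the first *Peer Activate* session (feasibility".
- The Implementation Outcomes table says "Feasibility measured using qualitative feedback and quantitatively as the % of patients who agree to participate in the intervention", again with a 75% threshold, and adds qualitative coding.

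Neither feasibility statement names its denominator. The acceptability row of the same table does: "quantitatively as the % of patients enrolled who attend".

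On numbers, the protocol says under Enrollment Numbers that "our goal is to have at least 30 patients initiate the intervention". Under Rationale for Enrollment Numbers it cites attrition of about 20% and also "significant attrition between baseline and initiating the intervention".

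**The concern.** Agreeing to take part and attending a first session are different events at different times. Loss between them lowers the second proportion and leaves the first untouched. A report could therefore meet the 75% benchmark under one SAP sentence and miss it under the other, with nothing in either document to say which counts. The rule that the SAP presents as set in advance is also not the one in the protocol's hypothesis, so a reader cannot tell which was pre-specified. In a pilot whose main product is a set of milestone verdicts, that is worth settling for the primary one.

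**Working it through.** **Are the two rules the same event?** The protocol gives this order:

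1. Discussion with a team member, then an invitation to consent: "based on continued interest, the participant will be invited to complete the informed consent process" (Recruitment).
2. Verbal consent to the study, before baseline (Recruitment and Screening; Consent Process). This is the only act of agreement described.
3. Baseline assessment, after which some consenters can be found ineligible (Recruitment and Screening).
4. Sessions with the peer recovery specialist, after baseline (Intervention and Assessments).

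The agreement rule is settled at step 2 and the first-session rule at step 4. Losses at step 3, and between steps 3 and 4, affect only the second.

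**The plan's own arithmetic.** The 75% is a chosen benchmark, so there is no derivation behind it to reproduce. The only sample-size arithmetic does reproduce: 24 completers / (1 − 0.20) = 30 initiators.

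**First-session rule with enrolled patients as denominator.** This denominator is assumed by parallel with the acceptability row. If a fraction L of those enrolled is lost before session 1, the proportion is 1 − L, and the rule passes when L ≤ 25%. Taking 40 as the number enrolled (also an assumption):

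- Threshold: 0.75 × 40 = 30 patients.
- At the initiation goal: 30/40 = 75.0%, a pass with no margin.
- One fewer: 29/40 = 72.5%, a fail.

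The protocol elsewhere speaks of enrolling at least 30. With 30 enrolled, the rule would need 23 (23/30 = 76.7%; 22/30 = 73.3% fails).

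**How large is the loss?** The 20% can be read in two ways. If it covers loss before the first session, 40 × 0.80 = 32 and 32/40 = 80%, a pass. If it is the loss from 30 initiators to 24 completers, as the arithmetic above suggests, the earlier step has no figure. Assumed range for 40 enrolled:

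| Loss before session 1 | Attend session 1 | First-session rule |
|---|---|---|
| 10% | 36/40 = 90% | pass |
| 20% | 32/40 = 80% | pass |
| 25% | 30/40 = 75% | pass, on the line |
| 30% | 28/40 = 70% | fail |
| 40% | 24/40 = 60% | fail |

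The agreement proportion is the same in every row.

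**First-session rule with the agreement rule's denominator.** If a share p agrees and a share s of those attends, the first-session proportion is p × s. To reach 75%, s must be at least 0.75/p. For assumed p of 75%, 80% and 90%, s must be at least 100%, 93.75% and 83.3%. On a shared denominator the first-session rule can only be the stricter one, because attenders are a subset of those who agreed.

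**The case against.** The best counter-argument is that the two phrases are a definition and its measure. The SAP table speaks of agreeing to the intervention, whereas verbal consent is to the study, and the enrolment target counts patients who start the intervention. Turning up to session 1 would then be a natural sign of agreement. This reading is reasonable, but neither document states it. Even if it were adopted, the SAP milestone would still differ from the protocol's hypothesis and would still lack a denominator.

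It is also fair to say that a changed verdict is shown only under assumed counts. Pairing 40 with 30 takes figures from two sections, and on one reading the 20% attrition passes both rules if agreement also reaches 75%. That limits the finding to a verdict that can differ, and does not support one that will.

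A reader might infer that refusals go unrecorded, so that the agreement rate cannot be computed. The documents do not support so flat a statement. Consent Process treats a patient who declines as a refusal and hence ineligible, and Confidentiality keeps reasons for ineligibility, so refusals are arguably retained. That retention sentence follows one about chart screening, which leaves its coverage of consent-stage refusals open. No section commits to counting invitations.

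**Conclusion.** The conflict stands as a matter of text: one primary outcome, two 75% rules, and no statement of which governs. It should be fixed. Under the first-session rule with 40 enrolled, the protocol's initiation goal leaves no margin (30/40 = 75.0%) and one patient fewer misses; a 20% loss would clear it at 80%. These figures depend on reading 40 as the number enrolled and on enrolled patients being the denominator, neither of which is stated.

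Two stronger readings are not supported. Because the SAP is dated September 2022 and written partly in the past tense, a reader might infer that the first-session rule was picked after results were seen. The tense suggests that data may already exist, but nothing shows when or why the wording arose. A reader might also infer an invalid inference or an inflated error rate. This is a single-arm descriptive pilot with no test attached to the benchmark, so what is at stake is the clarity of a milestone claim. The qualitative feasibility coding does not resolve it, since it does not say which percentage is compared with 75%.

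**What to change.** Correct the SAP's opening paragraph so that one feasibility benchmark is stated. It should be the protocol's agreement rule, which the SAP table already repeats, unless the sponsor can document that the first-session rule was pre-specified.

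- Give the numerator and denominator. For agreement, a workable form is patients who consent divided by eligible patients who discussed the study and were invited to consent. If agreement means some act other than verbal consent, name it.
- Keep consent refusers in the denominator even though Consent Process labels them ineligible; otherwise the proportion loses its meaning.
- Report first-session attendance among enrolled patients as a separately named uptake measure.
- If data are already collected, report both proportions with raw counts and the verdict under each, and do not select one rule after the fact. If the number invited was not kept, reconstruct it where possible and state the gap.

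The cost is a few sentences in the SAP and a little tallying. The downside is that the reported feasibility figure may be less favourable. No trial procedure changes.
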